9.7.4 Tertiary Efficacy Variables

9.7.4.1 Patient-Reported Outcomes (PRO)

The Haemo-QoL-A questionnaire is a validated hemophilia-specific health-related quality of life questionnaire for adults (Rentz, 2008). It consists of 41 questions covering six domains (Physical Functioning, Role Functioning, Worry, Consequences of Bleeding, Emotional Impact and Treatment Concerns). Items are answered on a 6-point Likert-type scale, ranging from 0 (None of the time) to 5 (All of the time). Higher scores mean better health-related quality of life or less impairment for a particular subscale (Haemo-QoL Study Group, 2017). Details regarding the Haemo-QoL-A assessment will be included in the On Site File Binder.

The EQ-5D-5L instrument is a self-reported questionnaire designed to measure general health status (The EuroQol Group, 1990) (Brooks, 1996). The EQ-5D-5L is composed of 2-parts: a descriptive system that assesses 5 levels of perceived problems (mobility, self-care, usual activities, pain/discomfort, and anxiety/depression) in 5 dimensions and the EQ visual analogue scale (EQ VAS) assessment for overall health. A sample copy of the EQ-5D-5L and additional information are provided in the On Site File Binder.

The Haemophilia Activities List (HAL) measures the impact of hemophilia on self-perceived functional abilities in adults (Van Genderen, 2006). The instrument consists of multiple domains including lying/sitting/kneeling/standing, leg and arm function, use of transportation, self-care, household tasks, and leisure activities where subjects are asked to rate their level of difficulty with activities of daily living on a 6-point Likert-type scale from 1 (Impossible) to 6 (Never). For some items, subjects are given the choice to answer 'Not applicable'. A sample copy of the HAL and additional information are provided in the On Site File Binder.

The Work Productivity and Activity Impairment plus Classroom Impairment Questions: Hemophilia Specific (WPAI+CIQ:HS) instrument is designed to measure the effect of disease symptom severity on work productivity and classroom productivity (if applicable)

(Recht, 2014). The WPAI+CIQ:HS questionnaire yields scores related to work/classroom absenteeism, reduced on-the-job effectiveness, overall work/classroom impairment, and activity impairment. WPAI+CIQ:HS outcomes are expressed as impairment percentages, with higher numbers indicating greater impairment and less productivity (Reilly, 2002). A sample copy of the WPAI+CIQ:HS and additional information are provided in the On Site File Binder.

The Patient Reported Outcomes, Burdens, and Experiences (PROBE) questionnaire is designed to investigate and directly probe patient perspectives on outcomes they deem relevant to their life and care. PROBE aims to develop a new global tool to enhance the direct patient-voice in health care decision-making (Chai-Adisaksopha, 2017). PROBE data collected in 270-301 will be shared with the Patient Outcomes Research Group (PORG) in order to facilitated validation of the tool; subjects may opt out of having their data used for this purpose. A sample copy of the PROBE questionnaire and additional information are provided in the On Site File Binder.

9.7.5 Immunogenicity

Immunogenicity assays will be performed on plasma and PBMCs. The assays will include detection of anti-AAV5 capsid and anti-FVIII total antibodies, as well as determination of neutralizing antibodies against FVIII (FVIII inhibitors) and against the AAV5 capsid (Transduction Inhibitors, TI). FVIII Inhibitors will be assessed using the Bethesda assay with Nijmegen modification. Any abnormality of the liver parameters will lead to a retrospective immunogenicity assessment to evaluate FVIII- and capsid-specific cellular immunogenicity. FVIII- and capsid-specific cellular immunity will be assessed by stimulated cytokine secretion using an ELISpot assay performed on collected PBMCs.

9.7.6 Pharmacodynamics

The FVIII protein concentration and activity level as measured by a validated immunoassay and by a validated FVIII activity assay, respectively, will be used for plasma profiles; FVIII protein and activity will be used to determine PD parameters.

9.7.7 Exploratory Assessments

Blood samples will be collected from subjects at the time points indicated in Table 9.1.1, Table 9.1.2, Table 9.1.3, Table 9.1.4, and Table 9.1.5 to evaluate biochemical, molecular, cellular, and genetic/genomic aspects relevant to hemophilia A, coagulation, and/or AAV gene transfer, and to develop assays used for these evaluations. Subjects may choose to opt out of the exploratory genetic/genomic research being done to study or try to discover genes that are not yet known to be associated with hemophilia A.

All biomarker samples collected in this study may be used for exploratory biomarker research, including evaluation of additional biomarkers not specifically listed in the protocol. In addition, samples collected for other purposes in this study may be used for exploratory research once testing for the primary purpose has been completed.

9.7.7.1 Optional Liver Biopsy

Subjects electing to undergo an optional liver biopsy are required to consent to the procedure and collection of tissue in the study ICF. The analysis of the optional liver biopsy is considered exploratory. Subject who elect to proceed will have a liver biopsy performed during Year 1 post-infusion, at or around Week 52, and/or during Years 2-5. Additional liver biopsies at times deemed to be clinically relevant (eg, decreasing FVIII at a time of increased ALT) may be pursued. Subjects will be asked to consent to the procedure for each liver biopsy performed during the study.

Subjects who consent to the procedure will have a liver biopsy via either transjugular or percutaneous (ultrasound-guided) route, according to the standard procedures of the institution. Two tissue cores will be harvested in the context of the optional liver biopsy. Subjects will be required to observe an 8-hour fasting period before the procedure.

Within 24 hours prior to the biopsy being performed, subjects must have a documented FVIII activity level of ≥ 50 IU/dL (or higher, depending on local guidelines and/or investigator discretion). FVIII activity levels for this purpose should be assessed at the local laboratory within 7 days before the biopsy and again on the day the biopsy, prior to the procedure. As needed, subjects may be treated with additional exogenous FVIII replacement products in order to increase their FVIII activity levels to an appropriate level, under the supervision/instruction of the investigator, to ensure the safety of the subject during the procedure. This exogenous FVIII usage (if performed) should be recorded in the eCRF FVIII infusion pages under the category "Surgery/Procedure".

Details on required procedures for the optional liver biopsy are outlined in Table 9.1.7. Subjects consenting to participate to the optional liver biopsy will undergo pre-biopsy assessments at least 28 days before the procedure, as follows:

- Physical examination
- Hematology, coagulation, chemistry assessments
- Liver tests
- Liver ultrasound (subject should fast at least 8 hours prior to ultrasound)
- FibroScan

Subjects consenting to participate to the optional liver biopsy will undergo pre-biopsy assessments at least 7 days before the procedure, as follows:

- Local FVIII activity level assessment
- Pre-biopsy consultation (with hepatologist and/or radiologist)

On the day of the biopsy, brief physical examination and liver and blood tests should be performed before the procedure (including hematology, coagulation, and chemistry). FVIII activity assessment should also be performed to ensure the subject has sufficient FVIII activity to protect against procedure-related bleeding (as discussed above). LT assessment and a whole blood draw for PBMC collection should be performed on the biopsy day or ± 1 week from the biopsy day.

The optional liver biopsy should be performed in the morning if feasible, and the biopsy procedure and follow-up care should be done according to the local standard of care.

Additional details for handling the biopsy specimens are provided in the Laboratory Manual.

Following completion of the biopsy, the subject should remain under observation in the clinic for at least 4-6 hours. Overnight post-procedure observation may be done at the investigator's discretion and/or according to local guidelines.

Clinically significant findings reported from the histopathological analysis of the biopsy sample are subject to AE reporting (Section 10). Such findings should be further assessed and followed as clinically appropriate to manage the subject's medical care. A hepatologist and/or other specialist clinicians should be consulted if required. In the event that fibrotic changes are observed on the biopsy sample, additional liver ultrasound, FibroScan and/or Enhanced Liver Fibrosis (ELF) testing (as regionally available and/or approved by HA) may be considered at the discretion of the investigator and/or hepatologist.

9.7.8 Safety Variables

Safety in this study will be determined from evaluation of AEs, clinical laboratory assessments with a particular attention to the liver function, vital signs assessments, physical examinations, and immunogenicity.

9.7.8.1 Adverse Events

The determination, evaluation and reporting of AEs will be performed as outlined in Section 10.

9.7.8.2 Clinical Laboratory Assessments

The scheduled clinical laboratory tests are listed in Table 9.7.8.2.1. Refer to the On Site File Binder for instructions on obtaining and shipping samples.

Any abnormal test results determined to be clinically significant by the Investigator should be repeated (at the Investigator's discretion) until: (1) the cause of the abnormality is determined; (2) the value returns to baseline or to within normal limits; or (3) the Investigator determines that the abnormal value is no longer clinically significant.

All abnormal clinical laboratory results should be initialed and dated by an Investigator, along with a comment regarding whether or not the result is clinically significant. Each clinically significant laboratory result should be recorded as an adverse event.

The diagnosis, if known, associated with abnormalities in clinical laboratory tests that are considered clinically significant by the Investigator will be recorded on the AE eCRF.

Blood Chemistry	Hematology	Urine Tests	Coagulation Screen including:
Albumin	Hemoglobin	Appearance	APTT
BUN	Hematocrit	Color	PT/INR
Calcium	WBC count	рН	TT
Chloride	RBC count	Specific gravity	
Total cholesterol	Platelet count	Ketones	
CPK	Differential cell count	Protein	
Creatinine	RBC indices (MCV and MCH)	Glucose	
CRP	ABO blood typing*	Bilirubin	
Glucose		Nitrite	
Phosphorus		Urobilinogen	
Potassium		Hemoglobin	
Total protein			
Sodium			
Uric Acid			

Table 9.7.8.2.1: Clinical Laboratory Tests

BUN, blood urea nitrogen; CPK, creatinine phosphokinase; CRP, C-reactive protein; PT, prothrombin time; APTT, activated partial thromboplastin time; RBC, red blood cell; WBC, white blood cell; TT, thrombin time; INR, international normalized ratio; MCV, mean corpuscular volume; MCH, mean corpuscular hemoglobin.

^{*}ABO blood typing assessment should be performed at Baseline, or at another regularly scheduled visit prior to the end of the subject's participation in the study.

In addition to scheduled clinical laboratory assessments, a fasting blood lipid panel (including triglycerides, total cholesterol, HDL cholesterol, and LDL cholesterol) will be assessed at the BMN 270 infusion visit. Subjects will fast for at least 8 hours prior to pre-infusion laboratory sampling on the day of the infusion visit.

In case of hypersensitivity or adverse drug reaction, safety assessment, including physical examination and vital signs, will be done and additional blood samples will be collected within 1 hour of the hypersensitivity reaction (eg, tryptase, C3, C3a, C4, C5, C5a, and cytokine bead array, as well as possible additional exploratory testing) and samples for IgE and cytokine bead array (and possible additional exploratory testing) between 8-24 hours after the reaction. In addition, a blood sample should be taken 1 week after the hypersensitivity reaction for assessment of the cytokine bead array.

At applicable sites, certain study assessments designed in the Schedule of Events may be performed by a mobile nursing (MN) professional at the patient's home or another suitable location, such as their school or office, to improve access and convenience for patients participating in the study. The Sponsor may select a healthcare company that will be responsible for providing MN services for participating sites (the MN vendor). The MN vendor is responsible for ensuring that all MN professionals are licensed, qualified, and in good standing, as per applicable regulations, and that appropriate background checks have been performed. If the investigator at a participating site determines that MN services are appropriate for a patient and the patient gives written informed consent to participate in MN visits, the MN network will communicate with the patient and the patient's site.

For all subjects, MN visits will be allowed for the Q4W (during Year 2) and Q6W (during Years 3-5) visits; the Q12W visits and End of Year visits during Years 2-5 will not be performed by an MN professional but will be done at the study site. For subjects who have enrolled in 270-301 following participation in 270-902, MN visits may also be available during Year 1 at Weeks 5, 7, 9, 11, 13, 15, 17, 19, 21, 23, 25, 27, 29, 30, 31, 33, 34, 35, 38, 42, 46, and 50 (as indicated in the Schedule of Events). At visits not specifically designated for MN eligibility (ie, visits where the subject is intended to return to the site for assessment), MN services may be used if the subject is unable to attend the site to complete the study visit during the acceptable window for that visit, upon prior approval by the Medical Monitor and discussion between the Medical Monitor and Investigator.

In the event that neither a lab-only visit or MN visit can be conducted for a post-infusion visit, the site should telephone the subject to collect adverse event, concomitant medication, and diary data (bleeding events and FVIII usage), in the interest of monitoring subject safety and welfare.

9.7.8.3 Liver and Hepatitis Testing

Subjects will be screened for evidence of previous or active hepatitis B or hepatitis C infection at Screening; hepatitis B screening should include HBsAg, HBsAb, and HBcAb. Subjects with documented results showing an absence of active hepatitis B or hepatitis C infection (as measured by positive DNA for hepatitis B or positive RNA testing for hepatitis C) 30 days prior to providing signed informed consent do not need to repeat those tests during the screening period.

Evidence of ongoing hepatitis B or hepatitis C infection is exclusionary. Subjects with a history of hepatitis B or hepatitis C infection prior to study entry will be tested for hepatitis B and hepatitis C reactivation at Week 16. Subjects with a history of hepatitis B or hepatitis C will be asked for information about the treatments received as part of their medical history assessment at Screening.

Subjects with a previous history of hepatitis B or hepatitis C who receive therapeutic oral corticosteroids prior to Week 16 do not need to complete the Week 16 reactivation assessment; instead, they will be tested for hepatitis B and hepatitis C reactivation at the time points listed in Table 9.1.6.

A liver ultrasound and liver tests (LTs) during Screening will identify any significant hepatic dysfunction.

LTs will be monitored on a regular basis; at each time point, the following LTs should be assessed:

Table 9.7.8.3.1: Liver Tests

Liver Tests (LTs)								
Alkaline Phosphatase	AST (SGOT)	Total Bilirubin	LDH					
ALT (SGPT)	Direct Bilirubin	GGT						

ALT, alanine aminotransferase; AST, aspartate aminotransferase; GGT, gamma-glutamyltransferase; LDH, lactate dehydrogenase; SGOT, serum glutamic-oxaloacetic transaminase; SGPT, serum glutamic-pyruvic transaminase

Elevated ALT levels (above the upper limit of normal range) should be evaluated according to the following plan (note that these evaluations may indicate additional testing of LTs and FVIII levels at unscheduled visits; these unscheduled laboratory tests may be completed by a mobile nursing professional at sites where the use of MN services has been approved):

Table 9.7.8.3.2: Evaluation of ALT Elevations

ALT Level	Work-Up
≥1.5x Baseline	 Continue to monitor LTs and FVIII per protocol (repeat within 7 days if next protocol scheduled visit is >7 days from the time of the reported ALT elevation)
- < 2x Baseline	• Consider evaluation to rule out alternative etiology (eg, concomitant medications, viral or autoimmune hepatitis, alcohol use, recreational drug use, special diets, strenuous exercise, prior and/or concurrent illnesses, exposure to environmental and/or industrial chemicals, etc.) (refer to Table 9.7.8.3.3)
	• If ALT is > ULN or > 1.5x baseline in 2 consecutive assessments within 24-72 hours and alternative etiologies have been ruled out, start oral corticosteroids upon consultation with the Medical Monitor (refer to Section 9.4.8.2)
	Consider liver biopsy at the discretion of the Investigator or Medical Monitor
≥2x Baseline	Repeat LTs and FVIII within 72 hours
or > ULN -	Continue to monitor LTs weekly until ALT is stable or improving
<3x ULN	Evaluate and rule out alternative etiologies (as above)
	Consult with Medical Monitor
	 If ALT is ≥ 2x baseline or > ULN - < 3x ULN in 2 consecutive assessments within 72 hours and alternative etiologies have been ruled out, start oral corticosteroids (refer to Section 9.4.8.2)
	Obtain other possibly relevant laboratory evaluations (albumin, PT/INR, CRP, etc.)
	Obtain complete blood count with differential to assess for eosinophilia
	Obtain PBMC to evaluate potential immune response (prior to starting oral corticosteroids)
	 If no improvement in 14 days, consider gastroenterology and/or hepatology consult, abdominal workup, imaging (including MRI or ultrasound), and/or liver biopsy as appropriate
≥3x ULN	Consult with Medical Monitor
	Evaluate and rule out alternative etiologies (as above)
	 Repeat LTs and FVIII within 48 hours, and continue with monitoring of LTs at least twice weekly for as long as the subject's ALT remains ≥ 3x ULN
	• In the event that ALT or AST is ≥3x ULN and total bilirubin is ≥2x ULN, albumin and PT/INR should also be obtained.
	• If ≥ 3x ULN in 2 consecutive assessments within 48 hours, start oral corticosteroids (refer to Section 9.4.8.2)
	Obtain other possibly relevant laboratory evaluations (albumin, PT/INR, CRP, etc.)
	Obtain complete blood count with differential to assess for eosinophilia
	 Obtain PBMC to evaluate potential immune response (prior to starting oral corticosteroids)
	 If no improvement in 14 days, consider gastroenterology and/or hepatology consult, abdominal workup, imaging (including MRI or ultrasound), and/or liver biopsy as appropriate

When ruling out alternative viral or autoimmune hepatitis as part of the elevated ALT workup, the following tests should be performed:

Table 9.7.8.3.3: Viral and Autoimmune Hepatitis Testing

Viral Hepatitis Workup Testing	Autoimmune Hepatitis Workup Testing
Hepatitis A	Smooth muscle antibody
Hepatitis B	Mitochondrial antibody
Hepatitis C	Liver/kidney microsomal antibodies
Hepatitis E	Antinuclear antibody (ANA) HEP-2
Cytomegalovirus (CMV)	
Epstein-Barr virus (EBV)	
Herpes simplex virus (HSV) 1 & 2	

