Each subject will have comprehensive surveillance monitoring of LTs (once per week for Weeks 1-36, and then once every 2 weeks from Weeks 37-52) during Year 1. LTs will be monitored every four weeks during Year 2 and then every 6 weeks during Years 3-5 post-dose in the safety extension; the frequency and duration of LT testing may be changed based on discussion between the Medical Monitor and the Investigator, review of subject data, and/or by independent DMC feedback.

There will be a detailed assessment of cellular and humoral responses to AAV5 capsid and FVIII protein.

NAME OF COMPANY	SUMMARY TABLE	FOR NATIONAL
BioMarin Pharmaceutical Inc.	Referring to Part of the	AUTHORITY USE
[name]	Dossier:	ONLY:
[name]		
	Volume:	
NAME OF FINISHED PRODUCT:		
MN 270	Page:	
NAME OF ACTIVE INCREDIENT.		
NAME OF ACTIVE INGREDIENT:	Reference:	
AAV5-hFVIII-SQ		

Pharmacodynamics:

The FVIII protein concentration and activity level as measured by a validated immunoassay and a validated FVIII activity assay, respectively, will be used for plasma profiles; FVIII protein and activity will be used to determine PD parameters.

STATISTICAL METHODS:

Sample Size

Approximately one hundred and thirty (130) subjects may be dosed in the study. The sample size for this study is based on clinical and statistical considerations in order to provide sufficient data to assess both safety and efficacy of BMN 270.

For the primary endpoint, a sample size of 130 will provide at least 95% power to demonstrate that the change in hFVIII activity during Weeks 49-52 from baseline is greater than 0, assuming an effect size of 0.6, using a one-sample t-test with a 2-sided significance level of 0.05.

For the secondary endpoints, the analyses will be performed utilizing exogenous FVIII use and bleeding episode data from the 110 subjects whose baseline data will be prospectively collected for approximately 6 months in the non-interventional study 270-902, prior to their enrollment in 270-301. An analytic sample size of 110 will provide at least 95% power to demonstrate that the change in the annualized utilization (IU/kg) of exogenous FVIII replacement therapy during Week 5 to Week 52 post-BMN 270 infusion from baseline is less than 0, assuming an effect size of 0.6, using a one-sample t-test with a 2-sided significance level of 0.05.

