Exploratory biomarker assessments ^d				X		X		X		X		X
PBMC Collection (for determination of FVIII and Capsid specific cellular immunity)				X				X				X
VWF:Ag				X								X
TGA Assay ^d				X		X		X		X		X
PCR of vector DNA in blood, saliva, urine, semen, and stools ^e				X		X		X		X		X
Haemo-QOL-A assessment												X
EQ-5D-5L												X
HAL												X
WPAI+CIQ:HS												X

		Year 1 – Weeks*										
Assessment	33 ^f	34 ^e	35 ^f	36	38 ^f	40	42 ^f	44	46 ^f	48	50 ^f	52
PROBE												X
Optional liver biopsy ^g					Perforn	n during	Year 1					X

^{*} Visit windows are \pm 48 hours through Week 36, then \pm 1 week until Week 52

- b Refer to Table 9.7.8.2.1 for laboratory assessments to be included, and to Table 9.7.8.3.1 for liver tests. LTs may be monitored more or less frequently (and in particular when ALT values are > ULN or ≥ 1.5x baseline value) based on discussion between the Medical Monitor and the Investigator and review of subject data, but LTs will be monitored at least twice weekly during periods when a subject's ALT is ≥ 3x ULN. Subjects with ALT > ULN or ≥ 1.5x baseline value during the study and either an alternative etiology considered or for further evaluation of the lab abnormality may undergo additional evaluations (eg, imaging studies including MRI or ultrasound, additional blood tests, and/or liver biopsy) at the discretion of the Investigator. Additional testing of FVIII and LTs during any study week may be performed if: (1) the ALT has increased to above ULN or increased by > 10 U/L from prior assessment; (2) Increases in ALT values from prior assessment are accompanied by declines in FVIII activity level; or after a discussion between the Medical Monitor and the Investigator based on discussion between the Medical Monitor and the Investigator.

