9.4.8.1 Concomitant Hemophilia Treatments

Subjects on prophylactic FVIII therapy will discontinue their regular treatment regimen starting 4 weeks after the day of infusion and switch to an "on-demand" schedule. FVIII replacement therapy can always be taken as needed by the subject for treatment of an acute bleeding episode; the subject must carefully record his treatment and bleeding episodes in his diary. Prophylactic FVIII use can be used on a case-by-case basis and in consultation with the Medical Monitor to prevent bleeding in extenuating circumstances (eg, peri-operative).

In addition, information on FVIII usage and bleeding episodes by medical history must be well-documented and available and will be collected from subjects for the 12-month period immediately preceding study enrollment. Further information on the details that should be

provided as part of the subject's well-documented medical and FVIII usage history are provided in the On Site File Binder.

In order to enable rigorous comparisons of pre-study versus on-study FVIII usage and bleeding episodes, the Medical Monitor will review each screened patient's prior bleed and hemophilia medication logs to determine if they are of "high-quality". Elements that will be assessed to judge the quality of such historical data may include, but are not limited to, the following:

- Date, type (eg, joint, muscle, other), location of bleeds
- Date, name, dose (calculated in IU/kg), and reason for use (eg, usual prophylaxis, one-time prophylaxis, treatment for bleed, surgery) of hemophilia medications.

9.4.8.2 Therapeutic Glucocorticoid Treatment and/or Immunosuppressive Agent Treatment of Elevated Hepatic Transaminases

Refer to corticosteroid prescription guidelines for recommended monitoring for, and management of, potential side effects of corticosteroids, including guidance on medications that should be avoided during corticosteroid treatment.

Therapeutic oral corticosteroids (prednisone or converted equivalent) should be initiated when either of the following occurs post-BMN 270 infusion in any subject and after consultation with the Medical Monitor (or their designee):

- ALT > ULN or $\ge 1.5x$ baseline value in 2 consecutive assessments within 72 hours and alternative etiologies have been ruled out, or ALT $\ge 3x$ ULN in 2 consecutive assessments within 48 hours (refer to Table 9.7.8.3.2)

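### In Table 9.7.8.3.2 the row for ALT 1.5x to <2x baseline does not order the retest that its own corticosteroid trigger needs, and it differs from Section 9.4.8.2

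*Protocol*

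**What the plan says.** Section 9.7.8.3 of Protocol Amendment 6 gives the work-up of raised ALT in Table 9.7.8.3.2, which has three rows.

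- **ALT at least 1.5x but below 2x baseline.** Retest: "Continue to monitor LTs and FVIII per protocol (repeat within 7 days if next protocol scheduled visit is >7 days from the time"; the clock starts when the raised ALT is reported. Trigger: ALT above ULN or more than 1.5x baseline "in 2 consecutive assessments within 24-72 hours and alternative etiologies have been ruled out, start oral corticosteroids upon consultation with the Medical Monitor".
- **ALT at least 2x baseline, or above ULN but below 3x ULN.** Retest: "Repeat LTs and FVIII within 72 hours". Trigger: two consecutive results within 72 h.
- **ALT at least 3x ULN.** Retest: "Repeat LTs and FVIII within 48 hours". Trigger: two consecutive results within 48 h.

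The sentence that introduces the table limits the plan to ALT above ULN.

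Section 9.4.8.2 states the corticosteroid criterion separately: ALT above ULN, or at least 1.5x "baseline value in 2 consecutive assessments within 72 hours and alternative etiologies have been ruled out", or at least 3x ULN twice within 48 h. It also asks for a confirmatory ALT draw where possible before treatment, without a time limit.

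The Synopsis sets scheduled liver tests in Year 1 at "once per week for Weeks 1-36, and then once every 2 weeks from Weeks 37-52". The windows in Table 9.1.4 are ± "48 hours through Week 36, then" ± 1 week to Week 52.

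**The concern.** A site that follows the lowest row exactly will usually not hold the two closely spaced results on which that row makes treatment depend. The row leaves it to the site whether to add an unscheduled draw, so two sites can both comply with the text and manage the same patient differently.

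The protocol itself gives the reason this matters. The Amendment 6 rationale says the revised ALT guidance should encourage earlier corticosteroid treatment and may better preserve FVIII expression. FVIII activity in Weeks 49-52 is the primary endpoint. The lowest row is where the reduced threshold takes effect, and it is the only row whose ordered retest does not serve its trigger.

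**Working it through.** The plan states no figure here to reproduce. The check compares the spacing of the required tests with the 24-72 h that the trigger allows.

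**1. Retest against trigger, row by row (Table 9.7.8.3.2)**

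| Row | Retest ordered | Trigger interval | Match |
|---|---|---|---|
| 1.5x to <2x baseline | per schedule, or within 7 days (168 h) | 24-72 h | no |
| ≥2x baseline, or >ULN to <3x ULN | within 72 h | within 72 h | yes |
| ≥3x ULN | within 48 h | within 48 h | yes |

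**2. Spacing of consecutive scheduled tests**

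Shortest gap = nominal gap − window of the earlier visit − window of the later visit. Windows come from Tables 9.1.2 to 9.1.5: ±48 h to Week 36, ±168 h to Week 52, ±336 h in Years 2-5.

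| Pair of visits | Nominal gap | Shortest gap |
|---|---|---|
| Day 4 to Day 8 | 96 h | 96 − 48 − 48 = 0 h |
| Weekly, to Week 36 | 168 h | 168 − 48 − 48 = 72 h |
| Week 36 to 38 | 336 h | 336 − 48 − 168 = 120 h |
| Every 2 weeks, Weeks 38-52 | 336 h | 336 − 168 − 168 = 0 h |
| Every 4 weeks, Year 2 | 672 h | 672 − 336 − 336 = 0 h |
| Every 6 weeks, Years 3-5 | 1008 h | 1008 − 336 − 336 = 336 h |

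Weekly visits reach 72 h only when one is a full 48 h late and the next a full 48 h early.

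**3. Chance that a pair falls in 24-72 h**

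Assumption: visit times are independent and uniform within their windows. The documents give no distribution. Where the nominal gap *g* is twice the window, the spacing is triangular on 0 to 2*g*, and the chance is (72² − 24²) / (2*g*²) = 4608 / (2*g*²).

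- Day 4 to Day 8, *g* = 96: 4608 / 18,432 = 25%.
- Weeks 38-52, *g* = 336: 4608 / 225,792 = about 2%.
- Year 2, *g* = 672: 4608 / 903,168 = about 0.5%.
- Weekly visits: 0, because only the boundary value is possible. Week 36 to 38 and Years 3-5: 0.

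**4. The 7-day repeat**

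When the next visit is more than 7 days away, the row orders a repeat within 168 h. This is the operative rule for most of the period after Week 36. A repeat drawn at 24-72 h meets both instructions. If its timing were uniform over 0-168 h, the chance would be (72 − 24) / 168 = 48 / 168 = 29%.

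**5. Who is left in the gap**

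The second row is entered at 2x baseline or above ULN. A subject at 1.5x to <2x baseline who is also above ULN (and below 3x ULN) fits both rows, and the second orders a repeat within 72 h. The subject for whom no short repeat is ordered is therefore the one at 1.5x to <2x baseline and not above ULN. The lead-in to the table does not cover that subject at all, yet the row defines him by baseline alone. The lowest row's trigger also names ALT above ULN, which is the next row's entry condition.

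**6. Against Section 9.4.8.2**

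The table row uses 24-72 h and more than 1.5x baseline. Section 9.4.8.2 uses within 72 h and at least 1.5x. Two results less than 24 h apart, or exactly at 1.5x baseline and not above ULN, meet the section but not the row.

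**The case against.** A reader might infer that subjects in this band can never meet the trigger. The documents do not support that. A repeat within 7 days may be drawn at 24-72 h, and the windows allow a qualifying pair at some visits. Extra testing is also open to the site: the schedule footnotes allow more frequent liver tests, naming this same threshold, the table's lead-in foresees unscheduled draws, and Section 9.4.8.2 asks for a confirmatory draw where possible. These points defeat any claim of impossibility. They do not close the gap, because none of them requires a second draw within 72 h.

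The second row is the stronger answer. Anyone above ULN gets an ordered repeat within 72 h, or 48 h at 3x ULN, and if the lead-in is read literally that is everyone the table covers. This stands, and it confines the problem to ALT at or below ULN. It does so only by making the lead-in contradict the row.

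A reader might also infer a wide effect, because Section 7.4 reports ALT elevation in most subjects. That statement covers all elevations and says nothing about this narrow band. Medical Monitor consultation before treatment limits variation between sites, but it does not supply the missing result. Enrolment was complete when Amendment 6 was issued, and Section 7.4 places ALT elevations shortly after dosing, so the number of Year 1 decisions this row governed is unknown. The Week 52 analysis was still to come, and liver monitoring runs to Year 5.

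The difference between >1.5x and ≥1.5x matters only at exact equality and is editorial.

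**Conclusion.** The point holds as a mismatch within one row and between that row and two other places in the protocol. For ALT at least 1.5x but below 2x baseline, the row does not require the retest its trigger needs. Required testing will usually fail to yield a qualifying pair: the chance is nil for weekly visits apart from the 72 h boundary, about 2% for scheduled 2-weekly pairs, and about 29% where the 7-day repeat applies. Day 4 to Day 8 is the main exception among scheduled pairs, at about 25%. These percentages rest on the uniform-timing assumption. The nominal gaps of 168 h and 336 h do not.

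The effect falls mainly on subjects not above ULN, and the documents do not say how many there are. No effect on the primary result can be calculated, and sample size, power and type I error are untouched. The correction is worth making because the row works against the amendment's own stated aim and leaves handling to each site's reading.

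**What to change.** Reconcile four elements of the lowest row of Table 9.7.8.3.2: the retest interval, the trigger interval, the sign at 1.5x baseline, and the overlap with the next row for subjects above ULN. Bring the table's lead-in and Section 9.4.8.2 into line in the same step, so that all three describe the same subjects and the same criterion, and the retest ordered is the one the trigger needs. Which interval and threshold to adopt is a clinical decision for the sponsor, and none is proposed here.

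The cost is a correction to one table and its lead-in, a matching edit in Section 9.4.8.2, and a clarification to sites. No analysis changes.
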